Tobacco Cessation in Public Housing

NCT04889638

1/10/2024

Date: 01/10/2024

Principal Investigator: [name]

Application Number: IRB00224186

JHM IRB - eForm A – Protocol

- **Use the section headings to write the JHM IRB eForm A, inserting the appropriate material in each. If a section is not applicable, leave heading in and insert N/A.**
- **When submitting JHM IRB eForm A (new or revised), enter the date submitted to the field at the top of JHM IRB eForm A.**

1. Abstract

Lower socioeconomic populations continue to remain at high risk for tobacco use and suffer disproportionately from tobacco-related disease. Evidence is lacking of ways to optimally deliver behavioral and pharmaceutical-based cigarette smoking cessation interventions in real-world environments among disadvantaged cohorts where geographic, socioeconomic and technological disparities often undermine the effectiveness of evidence-based smoking cessation efforts. Our study focuses on residents of public housing in Baltimore City, a population who face multiple socioeconomic stressors and of whom up to 1/3 are assumed conventional cigarette users.

Our project uses a partnership between the Housing Authority of Baltimore City (HABC) and Johns Hopkins School of Medicine to enact a remote (off-site) cessation program in Douglass and Brooklyn Homes – two public housing complexes under the management of HABC. Our program will institute evidence-based practices in an accessible manner for the residents at both sites. Our program's key features include the remote recruitment, prescription, delivery and management of evidence-based nicotine pharmacotherapies, and provision of cessation counseling.

2. Objectives

To assess the feasibility of a remotely administered study design with a particular focus upon:

- a) Recruitment of smokers expressing a motivation to reduce or quit smoking
- b) Consent process
- c) Nicotine and non-nicotine pharmacotherapy selection, screening, prescription, delivery, storage management (participation education, side-effecting monitoring), and return of unused drug supplies
- d) Administration and perceived utility of motivational interviewing regarding smoking reduction and cessation
- e) Delivery of study reimbursement
- f) Utility of weekly text reminders of study participation and final endpoint
- g) Acceptability of outcome measures.
- h) Acceptability and evaluation of joint project oversight with HABC

3. Background

Date: 01/10/2024

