4TH STEP – DRUG AND STUDY VISIT REMINDERS

Participants will also be reminded that at all future study visits will occur remotely.

Participants will also be asked if they prefer to have the remaining study visits occur remotely by phone or video conferencing by Zoom. Participants will be notified that they will receive at least weekly text-messaging reminders providing updates regarding prescribed pharmacotherapies and study visit reminder dates/times.

They will be made aware that they will be contacted by text message (preferred) or phone on a scheduled basis as each week progresses. Messages will be of 2 types:

- Type 1: Reminder of the two offered dates & times of the following week's study visit video conference or phone call. The participant will choose one of the two dates for the study visit. Reminders will be sent 72 hours and 24 hours prior to each event.
- Type 2: For those prescribed Chantix®, follow-up will occur every 72 hours. The text or phone messages will ask if experiencing any medical issues on therapy [See Drugs/Substances/Devices and Risks sections in this protocol for more information on adverse effects]. The voice or text messages will state the question, “Are you experiencing any side effects or are you having any problems with taking Chantix?” If they text back “Yes”, the participant will receive a phone call by our research staff. The concerns will be reviewed with our medical specialist. The medical specialists may call the participant for further details and/or relaying the treatment plan. Concerns about the clinical status may warrant referral to the JHH Emergency Room or the Tobacco Treatment Clinic at Bayview Medical Center if acute medical care concerns arise.
 - If the medical recommendation is to discontinue BOTH the “acute” and “controller” pharmacotherapy, the patient will be disenrolled from the study. Participants who are disenrolled will be contacted by phone at the end of the intervention to employ the survey used at the final time point (See “Supplementary Document 6”). They will be provided contact information of local smoking cessation resources, including the state quitline ([name]) and Tobacco Treatment Clinic at Bayview Medical Center.
 - ❖ NOTE: We do not anticipate the discontinuation of both the “acute” and “controller” therapies based on our initial smoking cessation pilot at Douglass

Date: 01/10/2024

Principal Investigator: [name]

Application Number: IRB00224186

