(see Preliminary data). Based on the low frequency of observed side effects, there is a very low likelihood of a participant not being a good candidate for NRT patch (“controller”) or NRT gum/lozenge (“acute”). This means that an individual who may not qualify for “Chantix” could be converted “NRT transdermal patch”, while continuing on their NRT gum/lozenge.

TIME POINT 4 – follow/up visit

WEEKLY FOLLOW-UP VISIT

Each weekly follow-up visit will occur remotely based on participant preference for a videoconference platform (Zoom) or mobile phone. Two separate times for study visit will be offered to allow participants the option to choose a time more preferable to their schedule. If Zoom is not preferable or communication issues arise, standard audio phone-based options without video capacity will be instituted. There will be NO video or audio recordings of any of the study visits. Paper or electronic copies of participant answers will be stored in CRMS.

The intervention at these follow-up visits will have 4 key features:

1. Survey completion that contains questions about interval smoking characteristics (see “Supplementary Document3”).
2. Pharmacotherapy education that reinforces appropriate medication administration and commonly observed side effects. ***See Drugs/Substances/Devices and Risks sections in this protocol for more information on side effects.***
3. Cessation-directed motivational interviewing

1ST STEP – CONFIRMATION AND SURVEY SCREENING

- Participants will check-in with research staff to confirm that they were enrolled at the baseline study event (Week 0).
- A short survey (approximately 5 minutes) will be undertaken to acquire key smoking characteristics (see “Supplementary Document3”). The survey will ask about the usage of the prescribed pharmacotherapies and possible explanations for non-optimal adherence. The survey will also query the degree of nicotine dependence. The study follow-up visits are using shortened surveys to capture immediately relevant study outcomes, reduce study fatigue, and to improve participant acceptability of the project.

Surveys will be displayed on the video conference call if Zoom is the preferred modality for the study. For participants with difficulty reading the survey, the questions will be read aloud and the responses will be recorded. For phone-based visits, our research team will read the questions aloud and record the answer choices.

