- We will also confirm if any updates in contact information has occurred.

2ND STEP – DRUG EDUCATION AND SIDE-EFFECT MONITORING

Date: 01/10/2024

Principal Investigator: [name]

Application Number: IRB00224186

- Confirmation of the prescribed pharmacotherapies will be undertaken. This will also include self-reported frequency of daily usage of controller and rescue medications.

NOTE: We will confirm that NRT products and Chantix was prescribed to the correct participants through the completion of medication dispensing form (see “Supplementary Document 5”). The form also provides documentation that drug education has occurred.

- All participants will undergo repeat education on the appropriate means to self-administer the medications and commonly observed side effects.

We will again educate participants that they may avail of our 24-hour phone number to access research staff if concerns or questions arise regarding pharmacotherapy. Research staff will review concerns with medical specialists and respond through either text messaging and/or phone calls. If both controller and rescue medications are stopped, the patient will be disenrolled from the study. If disenrolled, they will be provided contact information of local smoking cessation resources in case they again start to smoke ([name] or tobacco treatment clinic at Bayview).

NOTE: All adverse effects or concerns about pharmacotherapy will be documented. The time, data, description of issue and response will be included in the documentation.

3RD STEP – CESSATION-DIRECTED MOTIVATIONAL INTERVIEWING

- Brief motivational interviewing (MI) delivered by research staff.

We will assist by enhancing willingness or motivation, as well as ability or confidence through the following methods:

- Offer personalized, relevant feedback about the importance of quitting
- Explore the individuals' perceived pros and cons of smoking and quitting
- Discuss the 4 R's of quitting tobacco use
 - Relevance: Help the individual identify why quitting tobacco is relevant to him/her.
 - Risk: Encourage the individual to verbalize possible negative outcomes of tobacco use.
 - Rewards: Help the individual identify the possible benefits of quitting tobacco use.
 - Roadblocks Help the individual to identify possible obstacles to quitting, including those from his/her past quit attempts.

4TH STEP – STUDY VISIT REMINDERS

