All elements of this time point mirror the description represented above (TIME POINT 4). The only difference is that one interval text messaging type will be used. *We will no longer ask Chantix® users about medication concerns every 72 hours, if they have not reported any adverse effects to date on therapy.* Participants will continue to receive reminders at 72 hours and 24 hours prior to the next scheduled follow-up study visit.

TIME POINT 6 – follow/up visit

WEEKLY FOLLOW-UP VISIT

All elements of this time point mirror the description represented above (TIME POINT 5)

TIME POINT 7 – FINAL follow/up visit

FINAL VISIT

This final study visit will occur by videoconference (Zoom) or a phone call. Two separate times for the study visit will be offered to allow participants the option to choose a time more

Date: 01/10/2024

Principal Investigator: [name]

Application Number: IRB00224186

preferable to their schedule. The intervention at this time point will have 3 key features:

1. Survey completion that contains questions about smoking characteristics and completion of open-ended questions that explore the feasibility of the study pilot (see “Supplementary Document 3”).
2. Referral to [name] or Tobacco Treatment Clinic at Bayview Medical Center if continued smoking cessation resources are requested
3. \$15 cash equivalent reimbursement for study participation.

1ST STEP – CONFIRMATION AND SURVEY SCREENING

- Participants will check-in with research staff to confirm their enrollment in the study.
- A short survey (approximately 5 minutes) will be undertaken to acquire key smoking characteristics (see “Supplementary Document 3”). The survey will ask the usage & frequency that the prescribed pharmacotherapies are being used, as well as query the degree of nicotine dependence over the 4-week pilot period. Surveys will be displayed on the video conference call if Zoom is the preferred modality for the study. For participants with difficulty reading the survey, the questions will be read aloud and the responses will be recorded. For phone-based visits, our research team will read the questions aloud and record the answer choices.

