Patients will undergo a multistep process to screen and monitor adverse effects on therapy. The medications prescribed & delivered based on initial screening will only be recommended for administration after participants undergo confirmation of appropriateness of drugs selection at the time of the baseline study visit (WEEK 3). Participants will be provided a 24-hour contact phone number to report concerns or adverse effects on therapy. All concerns will be reviewed by the PI within 24 hours of receipt.

All adverse events will be followed until resolution, stabilization, or until it has been determined that the study intervention or participation is not the cause. Further action and/or candidacy for an alternative pharmacotherapy (e.g. Chantix® changed to NRT patch) will occur under the direction of the medical specialists (PI).

Date: 01/10/2024

Principal Investigator: [name]

Application Number: IRB00224186

We will also ensure that Chantix is being administered to the correct participants and drug education is being delivered at each study visit through the completion of medication dispensing form (**see “Supplementary Document 5”**). The form requires the signature of the study team member who will verify administration and education of the medication to the correct participant.

c. Plan for reporting unanticipated problems or study deviations

All unanticipated problems and study deviations will be reviewed by the PI [name].

We have built the protocol to accommodate minor deviations. For example, our protocol is still maintained despite participants unable to attend the study visits or if all outcomes are not obtained during the 4 week trial. These will be reported in an IRB continuing review.

Major deviations will be reported immediately to the IRB. A major deviations are events that cause or could cause harm to subjects or others or that affect the fidelity of our research.

d. Legal risks such as the risks that would be associated with breach of confidentiality

Not applicable

e. Financial risks to the participants

There are no financial risks for participants

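### The only scheduled direct side-effect question described goes to Chantix users, so side effects in participants on NRT alone are likely to be under-recorded

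*Combined protocol and SAP*

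**What the plan says.** Section 2, objective (c), lists among the features to be tested for feasibility "storage management (participation education, side-effecting monitoring), and return of unused drug supplies".

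Section 4 then describes how side effects come to light:

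- **Message to Chantix users.** Time Point 3, 4th step: "For those prescribed Chantix®, follow-up will occur every 72 hours". The message asks: "Are you experiencing any side effects or are you having any problems with taking Chantix". Time Point 4 repeats it. At Time Point 5, "We will no longer ask Chantix® users about medication concerns every 72 hours", provided that they have reported no adverse effect so far.
- **Weekly visit, all participants.** Time Point 4, 2nd step, is headed as drug education and side-effect monitoring. It confirms the drugs, takes self-reported frequency of use, reminds participants of the phone number and states: "All participants will undergo repeat education on the appropriate means to self-administer the medications and commonly observed side effects".
- **Weekly survey, all participants.** Time Point 4, 1st step: "The survey will ask about the usage of the prescribed pharmacotherapies and possible explanations for non-optimal adherence".
- **Final visit, all participants.** Time Point 7, 1st step: "The survey will ask the usage & frequency that the prescribed pharmacotherapies are being used, as well as query the degree of nicotine dependence". Ten open-ended feasibility questions follow; their topics include experience with the medication.
- **Call-in line, all participants.** Section 8b: "Participants will be provided a 24-hour contact phone number to report concerns or adverse effects on therapy".

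Section 8b defines adverse events to include those on gum, lozenge and patch, and sets out a narrative report for NRT events. Section 4 requires every adverse effect or concern to be documented.

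**The concern.** The protocol says how an NRT side effect is to be written up, but its text does not say how participants on NRT alone are to be asked about one. A step that carries monitoring in its title describes teaching, a check on use and a phone number. Chantix users meanwhile receive a direct question on a fixed schedule.

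Two things are at stake. First, the pilot is meant to learn whether side-effect monitoring works when run remotely. For participants on NRT alone it would mostly learn how many people phone in. Second, any description of side effects by regimen would mix the effects of the products with the effect of being asked. A low count on the patch could mean few problems or few questions. The absence of formal testing (section 7c) does not remove this, because simple counts are affected as well.

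**Working it through.** The protocol states no figure to reproduce. The check sets the routes side by side and then counts the scheduled prompts.

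**1. Routes described in the text**

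| Route | Who is reached | Started by | Written as a direct side-effect question? |
|---|---|---|---|
| 72-hour message (Time Points 3 and 4; restricted from Time Point 5) | Chantix users | Study team | Yes |
| Weekly 2nd step: drugs, use, education, phone reminder | All | Study team | No |
| Weekly survey: use, reasons for poor adherence, dependence | All | Study team | No; indirect |
| Final survey and open-ended questions | All | Study team | No; indirect, once |
| 24-hour phone and text line | All | Participant | No |

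Only the first row both asks directly and is started by the team, and it omits participants on NRT alone.

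**2. Count of scheduled direct prompts**

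Inputs: one message per 72 hours = 3 days (Time Point 3, 4th step). Visits are taken as weekly, with baseline at day 0, Time Point 5 at day 14 and the final visit at day 28. The 4-week length and weekly visits are in section 4; the exact days are my reading.

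- Chantix user with no reported adverse effect: 14 / 3 = 4.7, so about 4 messages.
- Chantix user who has reported one, if messages continue to the final visit: 28 / 3 = 9.3, so up to about 9.
- Participant on NRT alone: 0.

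Between day 14 and day 28 a Chantix user with nothing reported also gets 0, the same as a participant on NRT alone. The imbalance between regimens therefore lies mainly in the first two weeks, plus the continued messages to those who have already reported something.

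**3. Where the difference arises**

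Visit content is the same for both regimens: no direct side-effect question is written for any of the four remote visits (Visits 3 to 6 in the visit list). The difference comes wholly from the messages between visits.

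**4. Same product, different asking**

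Every participant receives gum or lozenge. The first clause of the Chantix message asks about side effects in general, so it can bring out gum or lozenge effects in Chantix users. The same effects in a patch user meet no such prompt. Even for a product common to both regimens, ascertainment depends on the controller.

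**5. How many people**

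The protocol expects to follow 48 participants but gives no controller split. If 25% to 75% received the patch (an assumption), 48 × 0.25 = 12 to 48 × 0.75 = 36 people would have no scheduled direct question. The conclusion does not depend on this range.

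**The case against.** The strongest reply has four parts.

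- **The forms are not in the file.** Supplementary Documents 3 (surveys) and 5 (dispensing form) could contain a side-effect item. The step's title and the general promise of monitoring in section 8b suggest that staff may ask. This stands as a limit: the finding concerns the protocol text, and absence from the forms cannot be confirmed.
- **Other routes exist.** The weekly adherence item may well bring out NRT effects; section 3 attributes poor use in the 2019 pilot partly to mistaken beliefs about them. The closing questions cover experience with the medication, staff speak with participants weekly, and anything mentioned must be documented. This too stands in part. But someone who keeps using a product despite a side effect has no adherence failure to explain, and the closing questions come once and serve feasibility.
- **Extra prompts for Chantix are a reasonable response to risk**, given the warnings in section 8a. Agreed. That justifies the messages, but it does not explain why the visits that everyone attends have no written question.
- **No comparison is planned.** Section 7 plans no adverse-event analysis, there is no comparator, and controllers are chosen individually, so a Chantix-versus-patch contrast would be confounded anyway. This limits the consequence. It does not help a plain count of NRT side effects, or a judgement on whether monitoring was feasible.

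A reader might go further and infer that NRT users are never asked anything relevant, so that their side effects count only if volunteered. The indirect items contradict that. Nor can one say that nobody is asked about gum or lozenge, because the Chantix message is broad enough to include them.

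**Conclusion.** The point holds in a limited form. In the supplied text, the scheduled direct side-effect question reaches Chantix users (about 4 to 9 times) and participants on NRT alone 0 times. NRT side effects are likely to be under-recorded, and counts by regimen would not be comparable. This rests on weekly visit spacing and on the unsupplied forms containing no such item. If they do contain one, the remedy shrinks to stating it in section 4.

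The amount of under-recording cannot be estimated: the documents give neither a side-effect rate nor the share that indirect and volunteered routes would catch. It might also be tempting to say that the few side effects noted from the 2019 pilot (Time Point 3, 4th step) reflect the same weakness. The documents do not say how side effects were collected there, so that inference is unsupported.

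The primary outcome, feasibility from open-ended questions, is not undermined. What suffers is the evidence on one named feasibility target and the safety description. The change is worth making because it costs so little.

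**What to change.** At each remote visit (Visits 3 to 6, including the final one), put one identical question to every participant for each product prescribed, for example: *Since we last spoke, have you had any side effects or problems with your patch / gum / lozenge / Chantix?*

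- Record yes, no or not reached for each product, so that silence can be told apart from a clean answer.
- Document each yes through the existing section 8b narrative. Add a field for how the event came to light, since none of its seven listed items records this. Apply the narrative to Chantix events too, since it is worded for NRT events.
- Report events found by the visit question separately from those found by the Chantix-only messages and those volunteered. The visit question is then the one source that is alike across regimens.
- If Supplementary Document 3 or 5 already holds such an item, say so in section 4 and confirm that it goes to everyone.

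The Chantix messages can stay as they are. The cost is one added item on a survey of about 5 minutes and a wording amendment. Recorded side-effect counts will rise, and the report should say that this partly reflects asking.

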- Participants will also be asked 10 open-ended questions that will assess study feasibility (see “Supplementary Document 3”). Questions will be read aloud and the responses will be summarized solely in a written format by the research team. The questions explore participant thoughts on the objective, data collection, recruitment, pharmacotherapy experience (administration, education, delivery and monitoring), motivational interviewing, study schedule and text messaging/phone follow-up.

2ND STEP – UNUSED DRUG SUPPLIES

- Participants will be encouraged to return any unused drug supplies. The medications will be able to be returned in a pre-stamped envelope that was provided with the initial medication package prior to the study. The return envelope is to be labelled to the attention of the PI ([name]). The unused medications will be dropped off at a drug disposal unit at Johns Hopkins Monument Street Pharmacy.

3RD STEP – POST-PILOT CESSATION RESOURCES

- All participants will be provided contact information of local smoking cessation resources for continued participation in the cessation effort. They will be provided information for the state quit line ([name]) and the Tobacco Treatment Clinic at Bayview Medical Center.

4TH STEP – REIMBURSEMENT OF STUDY VISIT PARTICIPATION BY EMAIL OR

TEXT MESSAGING.

- \$15 cash equivalent reimbursement for study participation.

• ***Data and Safety Monitoring Plan***

For the proposed research, [name] will take the responsibility for coordinating and assuring data storage and access. We do not expect the project to produce more data than can be appropriately managed by the research team. This research will generate data resulting from surveys and questionnaires.

Clinical Research Management System (CRMS) is being used for data management and research implementation. CRMS will contain the following information:

- Protocol information from eIRB2
- Registry of study participants
- Management of study accruals
- Consent tracking
- Secure location for study-related documents (e.g. surveys, questionnaires and screening tools)
- Pre-configured and adhoc reports
- Multiple interfaces with Epic, including sending data to Epic about the study and the study participants

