7. STUDY STATISTICS

a. Primary outcome variable

The primary endpoint will be study feasibility. Feasibility will be measured using open-ended questions administered by the research team and targeting the study stakeholders (study participants, community stakeholders and research team). The answers will serve as a means to evaluate the need for further modification in the recruitment, screening, consent, study implementation and evaluation phases of future study testing..

b. Exploratory outcome variables

Pre- & post-changes in nicotine dependence levels – Results will be stratified by baseline smoking behaviors, sociodemographic characteristics and socioeconomic stressors. For group-wise comparisons, t-test or analysis of variance will be used. Regression analyses will be performed to investigate the relationship between baseline measures and changes in smoking characteristics as the pilot study progressed.

c. Statistical plan including sample size justification and interim data analysis

Date: 01/10/2024

Principal Investigator: [name]

Application Number: IRB00224186

This study will not be powered for significance. The primary purpose of this study is to assess feasibility of the pilot study design.

d. Early stopping rules

Not applicable

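### Participants' feasibility answers are kept only as a summary written by the team that delivers the programme, so softened criticism could not be checked

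*Combined protocol and SAP*

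**What the plan says.** Section 7a (Primary outcome variable) states: "The primary endpoint will be study feasibility". It continues: "Feasibility will be measured using open-ended questions administered by the research team", "targeting the study stakeholders (study participants, community stakeholders and research team". The answers are meant to show what should be changed before further testing. No count, rate, threshold or coding method is attached to the endpoint.

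The procedure for participants is in Section 4, Time Point 7, 1st step: "Participants will also be asked 10 open-ended questions that will assess study feasibility". The questions are read aloud, and "the responses will be summarized solely in a written format by the research team".

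On records, Time Point 4 states: "There will be NO video or audio recordings of any of the study visits". The same paragraph adds, for the weekly visits: "Paper or electronic copies of participant answers will be stored in CRMS". The Data and Safety Monitoring Plan has written material scanned into CRMS and then destroyed.

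On delivery, study staff hand over the medication (Time Point 3, Part 1). On-site research staff give the motivational interviewing at baseline (Time Point 3, Part 2, 3rd step), and research staff give it at the weekly visits (Time Point 4, 3rd step). Drug education is part of the baseline and weekly visits run by the team.

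**The concern.** The value of this pilot lies in what participants say did not work, because that is what the next version of the programme will be built on. Two steps stand between a participant's opinion and the record, and both are in the hands of the team whose work is being judged.

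- **Asking.** A participant may be reluctant to criticise counselling or education to a member of the team that provided it.
- **Recording.** A summary is an act of selection. The person writing it decides which remarks are worth keeping and how strongly to word them.

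If either step loses or softens a criticism, nothing in the record shows it. A later reader, or the team itself, has no source text to return to.

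**Working it through.** The plan gives no figure for this endpoint, so there is nothing to recompute. The check is to set the relevant sections side by side.

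**1. What is the only planned record of the participants' answers?** Time Point 7 says the answers are summarised. The ban on recordings in Time Point 4 covers every study visit. Paper is scanned and then destroyed, but the scan is of whatever was written, and that is a summary. So the summary is the only record described.

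**2. Who asks, and about whose work?** The table sets the topics listed in Time Point 7 against who delivers each one and what other record the plan keeps.

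| Topic of the questions | Delivered by | Other record in the plan |
|---|---|---|
| Recruitment | Flyer and on-site housing coordinators; screening and consent by the research side | Accrual and consent tracking in CRMS |
| Drug delivery | Study staff | Participant's signature on receipt |
| Drug administration and monitoring | Research team | Weekly survey on use and reasons for poor adherence; logged concerns with date, description and response |
| Drug education | Research team | Dispensing form showing that education took place, not how it was received |
| Motivational interviewing | Research staff | None that captures the participant's opinion |
| Schedule, text and phone follow-up | Research team | None that captures the participant's opinion |

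For drug use and side effects, an over-favourable summary could be contradicted by other data. For opinions of the counselling, education, schedule and reminders, it could not. Section 2 lists the perceived utility of motivational interviewing and the utility of text reminders among the objectives, so these are not side issues.

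**3. Is any safeguard described?** The available documents mention no separation of interviewer from counsellor, no near-verbatim notes, no check of the summary with the participant, and no theme list or second coder.

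**4. How much of the endpoint is affected?** Participants are one of three sources in Section 7a. They are the only one with a described procedure. How community stakeholders' answers are collected and recorded is not stated. The third source is the research team's own view.

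**5. Can the bias be sized?** No. The documents give no rate of negative answers, no rate of loss and no binary acceptability measure. Any percentage would rest on assumed inputs and on an outcome the plan does not have.

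**The case against.** The strongest case on the other side has five parts.

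- **Internal interviewers are ordinary in a small pilot.** The plan says it is not powered, and its purpose is to learn what to change. This stands. It is a reason to ask for no outside interviewer and no recording, but it does not explain why only a summary should be kept.
- **Same team does not mean same person.** A reader might infer that the individual who counselled a participant also interviews that participant. The documents do not say so. They speak only of the research team, research staff or study staff. What they support is that no separation is planned. The record-keeping problem does not depend on this point.
- **The endpoint is wider than these 10 questions, and there are other data.** Both are true. A reader might infer that any distortion is undetectable, but the weekly surveys and logged concerns provide a partial check, as the table shows.
- **The first pilot reported plain criticism.** Section 3 lists under-use of nicotine replacement and poor delivery of counselling among findings that all stakeholders agreed on. Criticism can therefore get through, which argues against assuming a one-way upward bias. Section 3 does not say how those views were collected, so it does not validate the present method.
- **The wording may only exclude recording, and the instrument is in Supplementary Document 3.** The restriction to a written format can be read that way, and the supplement, which is not available here, may say how answers are entered. Even so, the protocol text says the responses are summarised, and the sentence on storing copies of answers in CRMS belongs to the weekly visits.

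**Conclusion.** The concern holds in a limited form. The participant part of the primary endpoint is asked and summarised by the team that delivers the programme, and the summary cannot be checked against what was said. The exposure is documented, but its size and direction are not and cannot be derived from the plan.

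A reader might go further and infer that recorded acceptability will be inflated by some number of points. The documents do not support that, because Section 7a defines no acceptability rate, threshold or go/no-go rule.

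The conclusion rests on two assumptions: that a summary means something less than a near-verbatim note, and that Supplementary Document 3 does not already require the latter. Severity is minor to moderate. The reason to act is that the improvement is cheap and the lost text could not be recovered afterwards.

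**What to change.** In Section 4, Time Point 7, 1st step, replace the summary with the following:

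1. Write each answer as close to word for word as possible during the call.
2. Read it back to the participant and correct it.
3. Store that text in CRMS as the source record.
4. Code the text afterwards against a list of themes fixed before the first final visit.

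Where staffing allows, have the 10 questions asked by a team member who did not counsel that participant. This is conditional because the documents give neither the size of the team nor its allocation to the two sites. Steps 1 to 4 work without it. They make the record checkable but do not by themselves remove a participant's reluctance to criticise.

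The cost is a few minutes on each final call, plus the coding time. On the plan's own expectation in Time Point 1, Note 1, that is about 60 × (1 − 0.20) = 48 calls, and fewer with later dropout. No recording is needed, and the note-taking and read-back need no extra staff. The downside is a longer call, against the plan's aim of keeping participant burden low.
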